5.2 Secondary objectives

- Changes in the Morisky Medication Adherence Scale (MMAS) at 12 months compared to month 3,
- Changes of the Treatment Satisfaction Questionaire for Medication (TSQM) over time,
- Changes in Rheumatoid Arthritis Disease Activity Index (RADAI) in patients with RA and if reasonable in patients with PsA,
- Changes in Bath Ankylosing Spondylitis Disease Activity Index (BASDAI) in patients with AS,
- Changes in Psoriasis Area and Severity Index (PASI) in patients with plaque psoriasis,
- Changes in Harvey-Bradshaw Index (HBI) for patients with CD,
- Changes in Partial Mayo Score (**PMS**) for patients with UC,
- Changes of the C-reactive protein (CRP) over time
- Changes of the Erythrocyte sedimentation rate (ESR) over time

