There is no recommendation regarding an appropriate amount of time for wash out of previous BDMARDs prior to initiating Adalimumab therapy. The determination of an appropriate time to initiate Adalimumab following discontinuation of another BDMARD is at the discretion of the physician. While individual patient variability can affect drug elimination, it is generally felt that a majority of a drug is eliminated after 4 to 5 drug half-lives. The health care professional may wish to consider this in determining the appropriate time to initiate Adalimumab therapy. Health care providers should use their knowledge of TNF α biology and best clinical judgment when determining an appropriate washout period of previous BDMARD therapy. AbbVie Austria's recommended wash out periods are: Etanercept received > 3 weeks (21 days) before 1st

_ 10

Adalimumab application Infliximab received > 8 weeks (56 days) before 1st Adalimumab

application

Schedule of Activities

ACTIVITIES	VISIT 1	VISIT 2	VISIT 3	VISIT 4	VISIT 5	EARLY
	SREENING					TERMI-
						NATION
TIME	Month 0	Month 3	Month 6	Month 9	Month 12	
Inclusion /Exclusion Criteria	x		57			
Written authorization to use data	X					
Patient demographics ^a	x		2			
TB: Chest X-ray	x					
TB: IGRA test	x		3			
TB: PPD skin test ¹	х					
ESR	x	x	X	X	X	x
CRP	X	X	X	X	X	х
RADAI ^c	x	x	x	x	x	x
BASDAI ^d	x	x	x	x	x	x
PASI ^e	x	x	x	X	x	x
Harvey-Bradshaw Index (HBI) ^f	x	x	x	x	x	x
Partial Mayo Score ^g	x	x	x	x	x	x
Beliefs about Medicines Questionnaire (BMQ)	x				×	x
Morisky Medication Adherence Scale (MMAS)		x	x	X	x	x
Treatment Satisfaction Questionnaire for Medication (TSQM)		x	x	x	x	x
Concomitant treatment	x	X	X	X	X	x
Adalimumabapplication ^b	x	X	x	x	X	x
Final Statement ^h					X	x

a. Patient demographics: year of birth, gender, race, disease, duration of RA,PsA,AS and previous as well as concomitant treatment

b. Adalimumabadministration: at screening information about dosing frequency and date of first as well as any further applications.

c. for RA and if reasonable for PsA, only

- d. for patients with AS only
- e. for patients with PsO only
- f. for patients with CD only
- g. for patients with UC only

Confidential Information

No use or disclosure outside AbbVie is permitted without prior written authorization from AbbVie

_ 11

abbvie

Adalimumab P13-562 Protocol

- h. Final statement shall also include a statement about pain-management with respect to a potential influence of adalimumab

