6.5.2.2 Follow-up visits

The total treatment period is max. 12 months for each patient.

Approximately 4 follow-up visits are expected over the 12 months period. These visits should occur at an interval of 3 months - "V2", "V3", "V4", "V5".

The visit schedule is to be decided by the investigator according to the routine clinical practice. Intercurrent visits will be documented using the CRF module with the next following visit

number, Visits V2,V3,V4,V5.

Follow up visits shall comprise the following:

V2: ESR,CRP, MMAS, TSQM, RADAI, BASDAI, PASI, HBI, PMS concomitant treatment, Adalimumab-application

- V3: ESR,CRP, MMAS, TSQM, RADAI, BASDAI, PASI, HBI, PMS concomitant treatment, Adalimumab application
- V4: ESR,CRP, MMAS, TSQM, RADAI, BASDAI, PASI, HBI, PMS concomitant treatment, Adalimumab application
- **V5:** ESR,CRP, BMQ, MMAS, TSQM, RADAI, BASDAI, PASI, HBI, PMS concomitant treatment, Adalimumab-application, final statement

Evaluation of the tolerability of the Adalimumab treatment

Any serious adverse events (**SAEs**) of the Adalimumab regimen will be collected throughout this study and 70-days following the last dose of Adalimumab.

Evaluation of the durability of the Adalimumab treatment

Any changes to RA, PsA, AS, PsO, CD or UC treatment and the type of change (dose modification or discontinuation) will be recorded in the data report form, whether the modifications relate to the use of Adalimumab or to the use of concomitant RA, PsA, AS, PsO, CD or UC treatments. If Adalimumab is temporarily interrupted or permanently discontinued before the end of the planned observational period of 12 months, the reason for interruption/discontinuation and the details on the subsequent RA, PsA, AS, PsO, CD or UC treatment, if applicable, will be recorded.

The next routine follow-up visit will be the post interruption/discontinuation visit (see 6.5.1.3).

6.5.2.3 Follow-up visit after temporary interruption or early permanent discontinuation of the Adalimumab treatment (Post interruption / discontinuation visit)

Follow-up visits after temporary interruption or early permanent discontinuation shall comprise the following:

ESR,CRP, Beliefs about Medicines Questionnaire (BMQ), Morisky Medication Adherence Scale (MMAS), Treatment Satisfaction Questionnaire for Medication (TSQM), concomitant treatment, Adalimumab application, final statement.

Evaluation of the tolerability since the interruption/discontinuation of the Adalimumab treatment

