11.1.2. Secondary end points

As secondary endpoints the following parameters will be evaluated: changes in the Morisky Medication Adherence Scale (**MMAS**) at visit 2, 3, 4 and 5, changes in the Treatment Satisfaction Questionnaire for Medication (**TSQM**) at visit 2, 3, 4 and 5, changes at the laboratory parameters such as C-reactive protein (**CRP**) and Erythrocyte sedimentation rate (**ESR**).

Changes in the Rheumatoid Arthritis Disease Activity Index (**RADAI**), Bath Ankylosing Activity Index (**BASDAI**), Psoriasis Area and Severity Index (PASI), Harvey-Bradshaw Index (HBI) and the Partial Mayo score (PMS) at visit 2, 3, 4 and 5. The quality of the analyses will depend on the fact that laboratory measurements are not stringent in the context of a non-interventional observational study. Tolerability and safety will be assessed by collection and classification of serious adverse events. Serious adverse reactions observed on treatment with Adalimumab will be described. The duration on treatment with Adalimumab until development

of a serious adverse reaction leading to Adalimumab discontinuation or until escape from treatment will be measured.

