11.2.2 Reason for switch to HUMIRA[®]

Never achieved satisfactory response:	У	n
Achieved satisfactory response initially, but lost it over time:	у 🗌	n
Discontinued treatment due to intolerance/side effect(s) :	у 🗆	n

Others

HUMIRA (Adalimum: For each vi	ab)
ESR (mm / 1 hr) (Erythrocyte Sedimentation Rate)	CRP (mg/l) (C-Reactive Protein)

Confidential Information No use or disclosure outside AbbVie is permitted without prior written authorization from AbbVie

P13-562 Protocol

Adalimumab

For Visit 1, Visit 5, and as appropriate for Early Termination 10-item Beliefs about Medicines Questionnaire (BMQ)

We would like to ask you about your personal views about your medicine and medicine in general. Please circle how you feel about each of the statements. There is no right or wrong answer, we are interested in your personal views.

Score:1-5 1. My health, at present, depends on my medicines **Confidential Information** No use or disclosure outside AbbVie is permitted without prior written authorization from Version: 6.5; 27 Oct 2016 Page 79 of 110

a. Strongly disagree b. disagree c. uncertain d. agree e. strongly agree

- My life would be impossible without my medicines
 a. Strongly disagree b. disagree c. uncertain d. agree e. strongly agree
- Without my medicines I would become very sick
 a. Strongly disagree b. disagree c. uncertain d. agree e. strongly agree
- 4. My health in the future will depend on my medicines
 a. Strongly disagree b. disagree c. uncertain d. agree e. strongly agree
- My medicines protect me from becoming worse
 a. Strongly disagree b. disagree c. uncertain d. agree e. strongly agree
- Having to take medicines worries me
 a. Strongly disagree b. disagree c. uncertain d. agree e. strongly agree
- 7. I sometimes worry about the long term effects of my medicines
 a. Strongly disagree b. disagree c. uncertain d. agree e. strongly agree
- My medicines are a mystery to me
 a. Strongly disagree b. disagree c. uncertain d. agree e. strongly agree
- 9. My medicines disrupt my life
 a. Strongly disagree b. disagree c. uncertain d. agree e. strongly agree
- I sometimes worry about becoming too dependent on my medicines
 a. Strongly disagree b. disagree c. uncertain d. agree e. strongly agree

Total 10-item BMQ Specific Score:

Adalimumab For Visit 2, Visit 3, Visit 4, Visit 5, and as appropriate for Early Termination Morisky Medication Adherence Scale (MMAS)

Patient self-reported Medication-taking-Scale: Scoring: high-low;

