YES = 0; No = 1

Range: 0-4

Confidential Information

- 1. Do you ever forget to take your medicine ?
- 2. Are you careless at times about taking your medicines ?
- 3. When you feel better do you sometimes stop taking your medicine?
- 4. Sometimes if you feel worse when you take the medicine, do you stop taking it ?

Total Score (sum of points) =

Adalimumab For Visit 3, Visit 5, and as appropriate for Early Termination Treatment Satisfaction Questionnaire for Medication (TSQM)

- 1. How satisfied or dissatisfied are you with the ability of the medication to prevent or treat your condition?
 - □1 Extremely Dissatisfied
 □2 Very Dissatisfied
 □3 Dissatisfied
 □4 Somewhat Satisfied
 □5 Satisfied
 □6 Very Satisfied
 - □7 Extremely Satisfied

obbvie Adalimumab

Adalimumab P13-562 Protocol

- 2. How satisfied or dissatisfied are you with the way the medication relieves your symptoms?
 - □1 Extremely Dissatisfied
 □2 Very Dissatisfied
 □3 Dissatisfied
 □4 Somewhat Satisfied
 □5 Satisfied
 - \Box 5 Satisfied
 - □6 Very Satisfied
 - □7 Extremely Satisfied
- 3. As a result of taking this medication, do you currently experience any side effects at all?
 - □1 Yes □0 No

Remark for the physician .: If YES please document on the SAE-Form !

- 4. How dissatisfied are you by side effects that interfere with your physical health and ability to function (e.g., strength, energy levels)?
 - □1 Extremely Dissatisfied
 - □2 Very Dissatisfied
 - □3 Somewhat Dissatisfied
 - □4 Slightly Dissatisfied
 - □5 Not at all Dissatisfied
- 5. How dissatisfied are you by side effects that interfere with your mental function (e.g., ability to think clearly, stay awake)?
 - □1 Extremely Dissatisfied
 - □2 Very Dissatisfied
 - □3 Somewhat Dissatisfied
 - □4 Slightly Dissatisfied
 - □5 Not at all Dissatisfied
- 6. How dissatisfied are you by side effects that interfere with your mood or emotions (e.g., anxiety/fear, sadness, irritation/anger)?
 - □1 Extremely Dissatisfied
 - □2 Very Dissatisfied
 - □3 Somewhat Dissatisfied
 - □4 Slightly Dissatisfied
 - □5 Not at all Dissatisfied

_ 82

Confidential Information

Adalimumab P13-562 Protocol

- 7. How satisfied or dissatisfied are you with how easy the medication is to use?
 - □1 Extremely Dissatisfied
 - □2 Very Dissatisfied
 - □3 Dissatisfied
 - □4 Somewhat Satisfied
 - □5 Satisfied
 - □6 Very Satisfied
 - □7 Extremely Satisfied
- 8. How satisfied or dissatisfied are you with how easy it is to plan when you will use the medication each time?

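### Two Appendix D forms contradict the plan for secondary endpoints: the visits at which TSQM is collected, and the time window and bleeding categories of the Partial Mayo score

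*Combined protocol and SAP*

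**What the plan says.** **TSQM in the plan.** Section 5.2 lists the secondary objective as "Changes of the Treatment Satisfaction Questionaire for Medication (TSQM) over time". In Section 11.1.2 the TSQM endpoint is followed by its visit list: "at visit 2, 3, 4 and 5, changes at the laboratory parameters such as C-reactive protein". The Schedule of Activities row "Treatment Satisfaction Questionnaire for Medication (TSQM") is marked at Visits 2, 3, 4, 5 and early termination, and not at Visit 1. Section 6.5.2.2 repeats this visit by visit, including "V2: ESR,CRP, MMAS, TSQM, RADAI, BASDAI, PASI, HBI, PMS concomitant treatment" and "V4: ESR,CRP, MMAS, TSQM, RADAI, BASDAI, PASI, HBI, PMS concomitant treatment".

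**TSQM on the form.** The Appendix D questionnaire is headed "For Visit 3, Visit 5, and as appropriate for Early Termination". The neighbouring forms agree with the schedule. One is headed "For Visit 2, Visit 3, Visit 4, Visit 5, and as appropriate for Early Termination Morisky Medication Adherence Scale" and the other "For Visit 1, Visit 5, and as appropriate for Early Termination 10-item Beliefs about Medicines Questionnaire (BMQ").

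**Partial Mayo in the plan.** Section 6.5.1 says the analysed score rests on an average of five measurements. Patients record stools and bleeding daily, and the stool-frequency and rectal-bleeding subscores are averaged over the five days before each visit. Days affected by bowel preparation or endoscopy are left out and replaced by earlier entries. The Physician's Global Assessment is a single rating that takes those five days into account. A bleeding score of 3 needs blood with at least half of the movements and also at least one movement of blood alone.

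**Partial Mayo on the form.** Appendix D bases the score on the previous 24 hours, with one entry per item. Its bleeding category 3 is the passage of blood alone, with no condition on the share of movements.

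**The concern.** A site completes the form in front of it, so where form and plan differ, the form may decide what data exist. For TSQM, following the heading drops months 3 and 9. Month 3 matters more. TSQM is not collected at Visit 1, so month 3 is the first value and the natural reference for change over time.

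For Partial Mayo, a one-day score is not the quantity that Section 6.5.1 defines for analysis, and it cannot be converted to a five-day mean afterwards. If some sites followed the text and others the form, a pooled mean would describe neither measure.

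Routine checks may not catch either problem. Section 9.0 says the study is not monitored and that entered data are checked for consistency. A questionnaire never issued at a visit leaves no entry to query.

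**Working it through.** The plan gives no figure of its own to reproduce here. It is descriptive, with no hypothesis, power or effect size (Section 11.2). The check compares the texts and adds simple counts and bounds.

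**1. TSQM visits**
- Schedule, Section 6.5.2.2 and Section 11.1.2: Visits 2, 3, 4, 5, so 4 assessments per patient.
- Form heading: Visits 3 and 5, so 2 scheduled assessments per patient, plus early termination.
- MMAS has the same planned visits, and its form spells out all four. The short TSQM list is therefore not a drafting shorthand.
- Planned enrolment is 140 (Section 6.2). Planned forms before dropout: 140 × 4 = 560. Under the heading: 140 × 2 = 280, a loss of 1 − 280/560 = 50%. The first value moves from month 3 to month 6.

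**2. Partial Mayo window**
- Inputs: three subscores of 0 to 3, so a maximum of 3 × 3 = 9. Two of them are averaged over five days in the text. The Physician's Global Assessment is held fixed.
- Five identical days: form minus text = 0.
- Last day 3 and four earlier days 0, with the last 24 hours being one of the five days: form 3, text 3/5 = 0.6, difference 2.4 per subscore. Two subscores: 2 × 2.4 = 4.8 of 9.
- The reverse (last day 0, four earlier days 3): form 0, text 12/5 = 2.4, difference −2.4 per subscore, or −4.8 in total.
- If endoscopy-related days are replaced by earlier entries, the last 24 hours can lie wholly outside the five averaged days. The difference is then up to 3 − 0 = 3 per subscore, 2 × 3 = 6 of 9.
- Hypothetical patient: stool 0, 0, 0, 0, 3; bleeding 0, 0, 0, 0, 2; global assessment 1. Text: 0.6 + 0.4 + 1 = 2.0. Form: 3 + 2 + 1 = 6. On the form's own bands these are no activity and moderate.

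**3. Bleeding categories, same day, no averaging**
- Take a day with six movements, one of blood alone and five clear. Share with blood: 1/6 = 17%, below 50%.
- Text: daily score 1, because the condition on the share of movements is not met.
- Form: 3, if category 3 is read as any passage of blood alone. The form also has a category for blood less than half the time and no rule for choosing between them, so 3 is one reading.
- Category difference on that reading: 3 − 1 = 2 points, separate from the window effect.

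**4. How many patients**
- TSQM concerns all 140. Partial Mayo concerns ulcerative colitis patients only, a subset of the 30 planned with Crohn's disease or ulcerative colitis.

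**The case against.** For TSQM the plan itself is not ambiguous: three places agree and one form heading differs. Section 10.0 refers to eCRF visit modules, and Appendix D does not show which modules carried the questionnaire. The live system may have been right. That stands, and it makes all TSQM data loss conditional. A reader might infer that half of the TSQM data were lost. The documents do not support that; they show a wrong heading and a need to check.

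For Partial Mayo, the bounds need an extreme one-day swing on both diary subscores, and nothing in the documents says how often that occurs. This also stands. A reader might take 4.8 as the maximum or as a typical error. It is neither: it depends on the last 24 hours being one of the five days, and the shift can be zero. Nor is the whole score averaged in the text, because the global assessment is a single rating.

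A reader might also infer that no diary was kept, since the Schedule of Activities has no diary line. The schedule lists visit activities and Section 6.5.1 requires daily records, so the omission proves nothing about conduct. Likewise, a form need not repeat every scoring rule.

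Two defences do not remove the point. Section 6.4 lets visit dates vary, but that does not change which questionnaire belongs to which visit. The study is descriptive, but a descriptive summary still needs one defined measure at stated visits.

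Finally, the remedy comes late. The Appendix D footers are dated 27 October 2016, and Section 6.4 estimates that inclusion ends in September 2016. With up to 12 months of observation per patient some visits remain on those dates, but a corrected form can help only those.

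**Conclusion.** The point holds as an internal inconsistency: both forms are wrong as written against the plan's text.

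- **TSQM:** if the heading was followed at every site, 2 of 4 scheduled assessments are lost, with at most 280 of 560 forms before dropout and no month-3 value. Whether this happened cannot be told from the documents.
- **Partial Mayo:** the form does not collect the score defined for analysis. With the global assessment fixed, the window alone shifts the total by 0 to 4.8 of 9 points when the last 24 hours is one of the averaged days, and by up to 6 when endoscopy-related days are replaced. The bleeding definition can add a same-day difference of 1 against 3 on one reading of the form. These are extremes.

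Both endpoints are secondary. A reader might carry the doubt about the forms over to the primary endpoint. For collection visits the documents do not support that, because the BMQ form heading matches the schedule. The point should be settled before analysis, because the data analysis plan is still to be written and the correction is small.

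**What to change.** **TSQM**
- Correct the form heading to Visits 2, 3, 4 and 5 plus early termination, for the visits that remain.
- Before the data analysis plan is fixed, confirm from the live eCRF at which visits the questionnaire was issued.
- Summarise TSQM by visit with n. If Visits 2 and 4 were not collected, restate the endpoint as the Visit 3 to Visit 5 change in patients with both values. Report early-termination values separately so that patients who discontinue are not dropped.

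**Partial Mayo**
- Establish which window and scoring rules sites used.
- Reconcile Section 6.5.1 with the Appendix D form, define one analysed score that matches what was collected, and do not pool the two versions.
- If the five-day version is kept, reconcile the diary with the Schedule of Activities and with Section 6.1, which rules out procedures beyond standard of care.

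**Cost.** One heading, one check of the eCRF modules, and a rewrite of either the Section 6.5.1 text or the form, plus a diary line if the five-day version stays. The report may have to say that early TSQM change was not measured in some patients, or that Partial Mayo is a one-day score.
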